10 DATA COLLECTION AND QUALITY ASSURANCE

10.1 Data Collection Forms

To maintain the confidentiality of the intervention participants, the study team will follow strict procedures that protect subject information. Information necessary for eligibility and enrollment will be stored in REDCap. REDCap is a secure web application designed to support data capture for research studies. It provides user-friendly web-based case report forms, real-time data entry with branching logic and validation (e.g. for data types and range checks), audit trails, a de-identified data export mechanism to common statistical packages (SPSS, SAS, Stata, R/S-Plus), procedures for importing data from external sources, and advanced features such as a data quality check module. The system was developed by a multi-institutional consortium initiated at Vanderbilt University. REDCap servers are physically located in the University of Michigan Medical School Information Systems (MSIS) data center. Application and database servers are on virtual machines (VM). Surveys will capture focus group participant demographics, specific diagnosis information for PLWD including diagnosis type and date of diagnosis; this information will also be collected and stored in REDCap. Participants' names and contact information will be stored in a secure, REDCap database, separate from their study data and only accessible to members of the research team for research purposes.

Focus group discussions will be recorded and then transcribed with identifiers removed and audio recordings will be destroyed. Transcriptions will be stored in password protected files.

Only data necessary for the intervention will be collected through EHR for subjects in aim 2 and 3 (demographics, medications, mailing address). Study participants will be identified using the EHR and data collected will be stored in REDCap. Outcome data will be collected from the EHRs and stored in REDCap, there will not be any further contact with study participants beyond the initial mailing of the intervention materials.

10.2 Data Management

Qualitative data from focus groups in Aim 1 will be stored in password protected files. All survey data from Aim 1 and EHR data from Aims 2 and 3 will be stored in REDCap. The system was developed by a multi-institutional consortium initiated at Vanderbilt University. REDCap servers are physically located in the University of Michigan Medical School Information Systems (MSIS) data center. The University of Michigan

team will sponsor REDCap accounts for each necessary member of the Henry Ford team. Only necessary study team members will have access. The Michigan Medicine team will lead data analysis.

10.3 Quality Assurance

10.3.1 Training

All staff have completed Program for the Education and Evaluation in Responsible Conduct of Research (PEERRS) and Good Clinical Practice trainings. Staff will follow quality assurance procedures to assure the accuracy and consistency of study data. Any adverse events that are serious and unexpected will be reported to study staff by participating clinics. Training on the importance of identifying any adverse events, including checklists, will be provided to clinic staff throughout the course of the study.

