Study participants will be identified using the EHRs and the intervention will consist of mailed materials to the participant—otherwise, the study team has no contact with study participants. Therefore, any potential adverse event reporting will come to the research team through clinics from which patients are identified. In the event of clinic staff notifying the study team of a serious and unexpected adverse event, the PI will follow the required reporting protocols detailed below.

7.3 **Adverse Events and Serious Adverse Events**

AE Definition: AE is any untoward or unfavorable medical occurrence in a human study participant, including any abnormal sign (e.g. abnormal physical exam or laboratory finding), symptom, or disease, temporally associated with the participants’ involvement in the research, whether or not considered related to participation in the research.

SAE Definition: SAEs consist of any adverse event that results in death; is life threatening or places the participant at immediate risk of death from the event as it occurred; requires or prolongs hospitalization; causes persistent or significant disability or incapacity; is another condition which investigators judge to represent significant hazards.

Unanticipated Problem (UP) Definition: any incident, experience, or outcome that meets all of the following criteria:

- unexpected, in terms of nature, severity, or frequency, given (a) the research procedures that are described in the protocol-related documents, such as the IRB-approved research protocol and informed consent document; and (b) the characteristics of the study population;
- related or possibly related to participation in the research;
- suggests that the research places participants or others at a greater risk of harm (including physical, psychological, economic, or social harm) than was previously known or recognized.

AEs for this study include:

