AEs for this study include a PLWD making medication changes without first consulting with a treating clinician. This may be revealed during the 2-month and 4-month chart reviews or by the prescribing clinician. Given risks associated with usual care (e.g., risk of respiratory suppression and death from common psychotropic-opioid combinations), while we will consider self-directed medication change an AE, in fact PLWD risk of medication-related adverse events would likely be lower than the risk from usual care (i.e., without change). Overall, we consider the potential for AEs to be low.

SAEs for this study include:

SAEs are not related nor anticipated as a result of this study. The study activities pose minimal risks. Death or hospitalization can reasonably be expected considering the study population includes persons living with dementia and those experiencing CNS polyRx. However, the study activities will not contribute to the death of participants; in fact, reducing burden of CNS-active medication should lower the risk of death. Prior deprescribing intervention studies in older adults demonstrate no impact on hospitalization or death.¹⁷¹⁵

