7.3.2 Follow-up for Adverse Events

Reporting Schedule:

- All adverse events that are serious (SAE) and unexpected (i.e., have not been previously reported for the study's intervention) will be reported to the IMPACT Collaboratory Regulatory and Data Team Leader ([name]), NIA IMPACT Collaboratory PO ([name]), and the IMPACT Collaboratory Safety Officer (SO) within 48 hours of the study's knowledge of SAE.
 - Only those adverse events that are serious (SAE), unexpected, and related to the intervention must also be reported to Advarra IRB. Unexpected and unrelated SAEs will be reported to Advarra IRB on a case-by-case basis if requested by the IMPACT Collaboratory Safety Officer (SO) or NIA IMPACT Collaboratory PO.
- All deaths will be reported to IMPACT Collaboratory Regulatory and Data Team Leader ([name]), NIA IMPACT Collaboratory PO ([name]), and the Safety Officer, [name] within 24 hours of study's knowledge of death.
 - Advarra IRB does not require the specific reporting of death outside of the SAE reporting requirement above, but they will be notified on a case-by-case basis if requested by the IMPACT Collaboratory Safety Officer (SO) or NIA IMPACT Collaboratory PO.
- All unanticipated problems (UPs) will be reported to the IMPACT Collaboratory Regulatory and Data Team Leader ([name]), Advarra IRB, NIA IMPACT Collaboratory PO ([name]), and the Safety Officer, [name] within 48 hours of the study's knowledge of the event.

- The summaries of all previously reported unexpected and related SAEs, deaths, and UPs, as well as all other SAEs and AEs will be reported to IMPACT Collaboratory Regulatory and Data Team Lead ([name]), Advarra IRB, NIA IMPACT Collaboratory PO ([name]), and the IMPACT Collaboratory Safety Officer, [name] at a minimum every 6 months, or at a frequency requested by the Safety Officer or NIA IMPACT Collaboratory PO.

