9 STATISTICAL CONSIDERATIONS

9.1 General Design Issues

For this nudge intervention, the primary clinical outcome will be change in the total standardized daily dosage (TSDD) of the medication classes contributing to CNS polyRx as measured in the EHR, from baseline to 4 months after sending the adapted intervention. We hypothesize a decline in the total standardized daily dosage (TSDD) following the nudge intervention. The presumed mechanism of the intervention is that the nudge educational tool will activate the dyad to discuss their current medication regimen with the prescribing clinician or a pharmacist. To determine whether the intervention has had this desired effect, as an implementation feasibility target, the team at each site will revisit intervention PLWD charts to complete an expedited chart review. We will complete initial reviews approximately two months after sending the tool and final review four months after sending the tool.

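### The rule for what clinics tell the study is narrower than what the study must report, and deaths and hospitalisations are not collected completely or equally in the two arms

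*Combined protocol and SAP*

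**What the plan says.** **What the study owes.** Section 7.3.2 states "All deaths will be reported to IMPACT Collaboratory Regulatory and Data Team Leader" and other named recipients, within 24 hours of the study's knowledge. It also requires summaries at least every 6 months, covering events already reported "as well as all other SAEs and AEs will be reported". By the definition in 7.3, an event that causes death or requires or prolongs hospitalisation is an SAE, and relatedness is not a condition for an AE.

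**What reaches the study.** Section 7.2 explains that the team has no contact with participants beyond the mailing, so "any potential adverse event reporting will come to the research team through clinics from which patients are identified". The Principal Investigator's action is then described for one case: "In the event of clinic staff notifying the study team of a serious and unexpected adverse event". Section 10.3.1 uses the same pair of conditions: "Any adverse events that are serious and unexpected will be reported to study staff by participating clinics". It goes on to promise clinic staff training and checklists on identifying any adverse event.

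**What counts as expected.** Section 7.3 says "Death or hospitalization can reasonably be expected considering the study population includes persons living with dementia". Section 7.3.2 instead treats an event as unexpected if it has not been reported before for the study's intervention.

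**Other routes.** For a patient changing medication without consulting a clinician, which 7.3 names as the study's own AE, the plan says "This may be revealed during the 2-month and 4-month chart reviews or by the prescribing clinician". On the review of charts for documented discussions, 9.1 says "the team at each site will revisit intervention PLWD charts to complete an expedited chart review". Section 9.5 plans a 4-month EHR query of all participants, for medication burden. The fields listed in 10.1 are demographics, medications and mailing address. Section 7.1 on safety parameters is marked not applicable, and 9.5 describes no safety analysis.

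**The concern.** A reporting duty is only as complete as the information that feeds it. Here the inflow rule has two conditions, serious and unexpected, while the outflow duty has neither for the periodic summaries and covers every death regardless of expectedness. A clinic that reads 7.3 and 10.3.1 together could reasonably conclude that a death or admission in a patient with dementia need not be passed on.

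The brochure is meant to prompt reductions in opioids, benzodiazepines, antiepileptics and antipsychotics in a frail population. The plan supports its safety case with hospitalisation and mortality findings from earlier deprescribing studies (7.2, 7.3), yet does not plan to collect either outcome. A sparse safety report could then be read as an absence of harm by the Safety Officer and in planning the full ePCT, when it might reflect only what was asked for. If intervention charts are opened more often than control charts, any count by arm built on these routes would also be skewed.

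**Working it through.** The plan gives no figure on this point, so the check sets the sections side by side. Illustrative arithmetic on assumed rates follows.

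**Step 1. Each event type against each route.**

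| Event | Owed under 7.3.2 | Clinic trigger if expectedness is judged against the population (7.3) | Clinic trigger if unexpected means not previously reported for the intervention (7.3.2) | Chart or EHR route stated |
|---|---|---|---|---|
| Death | Yes | No | Possibly | None |
| Hospitalisation | Yes, as an SAE | No | Possibly | None |
| Self-directed medication change, not serious | Yes | No | No | Chart reviews or prescribing clinician |
| Other non-serious AE | Yes | No | No | None |

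Under the first meaning, deaths and hospitalisations fall outside the trigger. The definition of an unanticipated problem in 7.3 also judges expectedness partly by the characteristics of the study population, so this meaning is not a stray remark. Under the second meaning a first death or admission could trigger notification, but a later one of the same kind could be regarded as already reported. Non-serious AEs meet the trigger under neither meaning.

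**Step 2. Balance between arms.** The clinic route in 7.2 is worded for all clinics. The conversation review in 9.1 is limited to intervention charts. The both-arm query in 9.5 concerns medications. Section 6.2.2 ties enrolment to being mailed the tool, so it is unclear whether control patients come under the safety reporting rules at all.

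**Step 3. How many events could be involved (assumed rates).** With n = 120 (9.2), expected events = 120 × r, and the chance of at least one = 1 − (1 − r)^120.
- Mortality 1%: 120 × 0.01 = 1.2 deaths; 1 − 0.99^120 = 70%.
- Mortality 5%: 120 × 0.05 = 6 deaths; 1 − 0.95^120 = 99.8%.
- Mortality 8%: 120 × 0.08 = 9.6 deaths; 1 − 0.92^120 is above 99.9%.
- Hospitalisation 10% to 20%: 120 × 0.10 = 12 to 120 × 0.20 = 24 patients.

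**Step 4. What a comparison by arm could show (assumed rates).** With 60 per arm and a two-sided 5% level,

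power = Φ{(|p2 − p1| − 1.96 √[2p̄(1 − p̄)/n]) / √[p1(1 − p1)/n + p2(1 − p2)/n]}, where p̄ = (p1 + p2)/2.

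For 10% v 20%: (0.10 − 1.96 × 0.0652)/0.0645 = −0.43, so power is 33%. With an assumed ICC of 0.05 and 30 patients per clinic, the design effect is 1 + 29 × 0.05 = 2.45, and n per arm becomes 60/2.45 = 24.5.

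| Rates | Power, no clustering | Power, ICC 0.05 |
|---|---|---|
| 5% v 10% | 18% | 10% |
| 10% v 20% | 33% | 16% |
| 15% v 30% | 50% | 24% |

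A harm table by arm would be descriptive.

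**The case against.** The best defence is that the plan is looser than it looks, not closed. Four parts of it stand.

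- A reader might infer that clinic notification of serious and unexpected events is the only inbound route. It is not: 7.3 names the chart reviews and the prescribing clinician, 6.1 schedules adverse events across months 7 to 12, and 10.3.1 trains clinics to identify any adverse event. However, 7.3 links its routes to self-directed medication change, 6.1 gives no method, and identifying an event is not the same as reporting it.
- A reader might infer that the duty to report deaths cannot be met. The clock runs from the study's knowledge, so every death the study learns of can be reported on time. What is not assured is that the study learns of each one.
- A reader might infer that deaths and admissions are excluded because they are called expected. The definition in 7.3.2 could make some of them notifiable, and nothing forbids a clinic from reporting more. The fault is that the term is ambiguous.
- A reader might infer that no comparison of harm by arm is possible. The 4-month query covers all participants, so one is feasible but unplanned. Nor is the field list in 10.1 clearly exhaustive: the same section mentions outcome data separately, and 6.2.2 adds diagnoses.

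It is also fair that this is a single mailed brochure, argued to be minimal risk, with a Safety Officer overseeing monitoring. That bears on how much safety work is proportionate. It does not reconcile an intake rule with a wider reporting duty.

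**Conclusion.** The point holds as an internal inconsistency with a practical consequence. The clinic trigger in 7.2 and 10.3.1 is narrower than the duty in 7.3.2, expectedness is used in two senses, and no stated route gives complete and equal ascertainment of deaths and hospitalisations in both arms. No harm summary by arm is planned. The mismatch rests on the text alone.

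Its size cannot be taken from the documents, which give no event rates. At an assumed 4-month mortality of 1% to 8%, about 1 to 10 deaths would occur among 120, and at least one is likely even at the low end (70%). An assumed 10% to 20% hospitalised would be 12 to 24 patients. These are events that might be missed, not a forecast that all would be. A reader might go further and predict an almost empty safety report, but that would require clinics, prescribers and chart reviewers all to pass on nothing, which the plan does not say.

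**What to change.** 1. Reconcile 7.2, 7.3, 7.3.2 and 10.3.1 so that clinics in both arms notify the study of all deaths and SAEs regardless of expectedness. State how non-serious AEs reach the 6-monthly summary.
2. Define *unexpected* once and use it throughout. Keep it for classifying and expediting events, not for deciding whether the study hears of them.
3. Add date of death, hospitalisations and ED visits to the EHR extraction for all 120 participants, and to the field list in 10.1. State in 6.2.2 or 7.3 that control patients are covered.
4. Add to 9.5 a descriptive table of these events by arm, with counts and denominators and no hypothesis test.

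The 4-month query already covers both arms, so the cost is a few more fields, a little more abstraction time and a short amendment. The comparison will have low power, and EHR extraction may miss events treated outside the two health systems; the report should say both. A side benefit is that date of death is needed to interpret a 4-month TSDD, since 9.5 does not say how a patient who has died is handled.

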10.3.2 Quality Control Committee

The Principal Investigator, [name], will be responsible for ensuring participants' safety on a daily basis. The study team will meet regularly to ensure safety and quality. In addition, the NIA IMPACT Collaboratory Safety Officer will oversee all data and safety monitoring activities for this study. The SO will act in an advisory capacity to the NIA Director to monitor participant safety, to evaluate the progress of the study, and to review procedures for maintaining the confidentiality of data, the quality of data collection, management, and analyses. Advarra IRB will conduct the ethical review required for the protection of human subjects. NIA PO, in consultation with DSMB chair, will make a determination regarding the level and format of data and safety monitoring this study requires, i.e., full DSMB oversight or monitoring by an independent SO.

10.3.3 Metrics

n/a

10.3.4 Protocol Deviations

Any unplanned deviations or departures from IRB approved protocol procedures will be reported to [name] and the Advara IRB.

10.3.5 Monitoring

Both the enrollment and implementation feasibility targets from Aim 2 will entail chart reviews for patients with dementia experiencing CNS-PolyRx. For each component, research assistants (RAs) will complete the first 20 chart reviews, which will then be reviewed by Drs. [name] and [name] (the UM and Henry Ford PIs, respectively) to assure appropriate and accurate data abstraction. The RAs will then complete further reviews independently.

11 PARTICIPANT RIGHTS AND CONFIDENTIALITY

11.1 Institutional Review Board (IRB) Review

This protocol and any future modifications will be submitted to the Advara IRB for

approval. Study team members will strictly adhere to IRB guidelines and policies.

11.2 Informed Consent Forms

Aim 1: Focus groups PLWD participants will have no more than mild dementia and participation in the focus group will present no more than minimal risk to the participants and the probability of experiencing minimal risks associated with this project are not greater than risks encountered in daily life. We will seek approval to waive documentation and include a comprehensive oral script for the PLWD-CP dyad. After completing the recruitment and screening procedures, interested and eligible individuals will have the option to receive a mailed and/or emailed a Consent Information Sheet (a simplified consent form with key information about the project and their involvement) before the focus group. At the beginning of the virtual focus group, study staff will review the main tenets of the Consent Information Sheet with all participants (PLWD-CP dyads) using a comprehensive oral script. Participants will also be informed that they may be asked to participate in a brief follow up phone call after the focus group (1-2 weeks following the discussion, and scheduled at the selected participant's convenience). The study team also allow participants to opt out of a follow-up phone call at the beginning of the focus group when staff summarizes the Consent Information Sheet. Participants will be encouraged to ask questions and verbal consent will be obtained. We have chosen this consent process to minimize participant burden and to ensure the cognitively impaired participants are not overwhelmed by information. This verbal consent process will make our recruitment processes more efficient. We will maintain a spreadsheet where we track participant IDs, we include a column for date of consent and consent provider. It should not be assumed that persons with mild cognitive impairment/early-stage dementia are unable to give consent. Our approach will make the consent process interactive and provide opportunities for the individual with dementia to demonstrate capacity to understand the study while not overwhelming with information. The research includes people living with dementia who will have capacity to provide informed consent. To ensure that the individuals understand their involvement in the research, our approach to informed consent will be pragmatic and interactive. We will use Talk Back to assess comprehension we will remind participants that their participation is voluntary and they are free to leave at any time. We will use the same approach (waiving documentation and using a comprehensive oral script) for obtaining informed consent for CP participants in the focus groups.

Aims 2 and 3: We will request a waiver of informed consent for PLWD participants in for the following reasons:

- *The research involves no more than minimal risk:* This is an educational intervention to prompt a discussion with the PLWD's clinician or pharmacist. Given the inclusion criteria—these are PLWD exposed to CNS polyRx—the "probability and magnitude of harm or discomfort anticipated in the research are not greater in and of themselves than those ordinarily encountered in daily life" given the adverse outcomes associated with the usual care (i.e., CNS polyRx) that establishes study eligibility.
- *The research could not practicably be carried out without the requested waiver or alteration:* Sending an informed consent document to PLWD describing the

deprescribing study could bias the control group by introducing them to the concept of deprescribing itself and interfere with the aims of this project.

- *If the research involves using identifiable private information or identifiable biospecimens, the research could not practicably be carried out without using such information or biospecimens in an identifiable format:* In order to determine feasibility, implementation, and primacy outcomes, the information must be in an identifiable format.
- *The waiver or alteration will not adversely affect the rights and welfare of the subjects:* The intervention is entirely comprised of education about appropriate medication use; generally providing additional, potentially actionable information to patients and families is a valuable goal in health care settings.
- *Whenever appropriate, the subjects or legally authorized representatives will be provided with additional pertinent information after participation:* At the conclusion of the study, we will send the intervention PLWD a one-page informational study summary. The summary will be written in accessible language and will include pertinent information and findings.

